#### 1.2.4 Residual Effect Period

The Residual Effect Period (REP) is the period after the last dose with measurable drug levels and/or pharmacodynamics effects still likely to be present. The REP of BI 1467335 is not known for this clinical trial. Therefore all AEs reported until the end of trial examination (last per protocol contact) will be considered on treatment. This rule will be also applied for subjects treated with phenelzine.

### 1.3 RATIONALE FOR PERFORMING THE TRIAL

An observed inhibition of MAO-A catalyzed kynuramine deamination by BI 1467335 was shown to be reversible. Although the in-vitro finding of a reversible inhibition of MAO-A was considered to be of remote clinical relevance, subjects and patients in ongoing studies were nevertheless advised to avoid the consumption of tyramine-rich food while on treatment with BI 1467335.

In case of a relevant MAO-A inhibition, dietary tyramine may escape from metabolic inactivation resulting in systemic noradrenergic effects, such as peripheral vasoconstriction, increase of systolic blood pressure or an increase of heart rate.

The planned study will be conducted as part of the overall risk assessment for treatment with BI 1467335 to conclusively demonstrate that multiple doses of BI 1467335 at therapeutic and supratherapeutic dose levels do not affect intestinal MAO-A activity in humans, thus excluding the necessity for dietary restrictions related to potential MAO-A inhibition.

#### 1.4 BENEFIT - RISK ASSESSMENT

Participation in this clinical trial is without any (therapeutic) benefit for healthy subjects. Their participation, however, is of major importance for the further clinical development of

Proprietary confidential information © 2020 Boehringer Ingelheim International GmbH or one or more of its affiliated companies

BI 1467335 in upcoming phase II and III studies. Subjects are exposed to risks of study procedures and risks related to the exposure to the trial medication.

#### Procedure-related risks

The use of an indwelling venous catheter or venepuncture for e.g. blood sampling may result in mild bruising, and in rare cases, in transient inflammation of the wall of the vein, or nerve injury, potentially resulting in paraesthesia, reduced sensibility, and/or pain for an indefinite period.

The total volume of blood withdrawn per subject during the entire study will be approximately 500 mL and thus does not exceed the volume of a normal blood donation (500 mL). No health-related risk to healthy subjects is expected from withdrawal of this volume of blood.

As part of the screening procedure, subjects will receive increasing oral doses of up to 700 mg tyramine. Under physiological conditions alimentary tyramine is completely inactivated by intestinal MAO-A, due to the limited amount of tyramine in food. For the challenge test, it is intended to exceed the individual intestinal MAO A capacity to achieve a systemic availability of oral tyramine. Tyramine acts as an indirect sympathomimetic agent by displacing noradrenaline from vesicles of adrenergic nerves. This leads to vasoconstriction and increase in blood pressure, and may cause headache and even hypertensive crisis [R19-1599]. Due to the design of the planned study with a shallow dose escalation, the stop of further tyramine dosing at TYR30, and the possibility to counteract the sympathomimetic effects with a non-selective  $\alpha$ -blocker, the risk of overshooting sympathomimetic effects (in particular the risk for hypertensive crisis) is considered remote. This should be also true for the occurrence of cardiac events by only including young healthy subjects at the age of  $\leq 45$  years.

#### Drug-related risks and safety measures

##### *BI 1467335*

BI 1467335 could cause on-target toxicity as its anti-inflammatory effects may reduce the immune response and thus worsen infections. However, a deleterious effect relating to a reduction in leukocyte or lymphocyte migration was not seen in any of the preclinical models and also not in patients or subjects exposed to BI 1467335.

The human safety and tolerability profile in male and female healthy subjects was satisfactory for multiple doses given over 28 consecutive days of up to 20 mg of BI 1467335 in study 1386.8 (see [Section 1.2](#)). There were no deaths or other serious adverse events. Adverse events, mostly reported as mild (CTCAE grade 1), had no apparent dose or exposure relationship. In view of the non-proportional increase of exposure there is an about 5-fold safety margin between the highest exposure at 20 mg q.d. and the exposure with 15 mg of BI 1467335 q.d. of the planned study.

It should be highlighted that the safety profile across all phase I studies was comparable. There were in particular no SAEs or reports of possibly dose limiting AEs.

Proprietary confidential information © 2020 Boehringer Ingelheim International GmbH or one or more of its affiliated companies

### *Phenelzine (Nardil®)*

Subjects may receive as positive control phenelzine for up to 19 days. The selected doses of 15 mg BID is below the recommended starting dose of 15 mg TID. The subjects to be included in the study will comply with the precautions or contraindications for phenelzine treatment (e.g. hepatic disease, alcoholism, diabetes mellitus, asthma, hyperthyroidism etc.).

Common side effects of phenelzine are related to CNS, gastrointestinal tract and may also include postural hypotension and edema [[R19-1594](#), [R19-1659](#)]. Subjects will be closely monitored for the occurrence of adverse events, with discontinuation of treatment in case of possibly drug related AEs of severe intensity.

### *DILI*

Although rare, a potential for drug-induced liver injury (DILI) is under constant surveillance by sponsors and regulators. Therefore, this trial requires timely detection, evaluation, and follow-up of laboratory alterations in selected liver laboratory parameters to ensure subjects' safety; see also [Section 5.2.6.1.4](#), adverse events of special interest.

### Summary of benefit-risk assessment

In previous trials in healthy subjects, multiple oral doses of up to 20 mg BI 1467335 were safe and well-tolerated. Because of the non-proportional increase of the exposure, this results in a huge safety margin between the exposure at the already tested maximum doses and the maximum dose of 15 mg of BI 1467335 in the planned study.

The treatment with phenelzine for up to 19 days using a dose regimen of 15 mg BID (daily dose 30 mg) is below the recommended starting dose and, based on a vast body of clinical experience, considered to be safe. However, as precautionary measure subjects assigned to phenelzine treatment will be hospitalized while on treatment.

The trial design is optimized to collect relevant information on intestinal MAO-A activity upon treatment with BI 1467335 without exposing participating volunteers to undue risk.

There is always the potential of serious adverse events (SAEs) occurring with intake of any trial medication. Risks to subjects will be minimized and addressed by eligibility criteria, safety laboratory examinations, ECG and vital sign measurements, in-house observation periods, and verbal communication concerning AEs.

If the investigator should have any clinical concern, the safety of the subjects will be of paramount importance. The investigator has the discretion to remove subjects from the study should there be any safety concerns or if the subject's wellbeing is at jeopardy.

## **2. TRIAL OBJECTIVES AND ENDPOINTS**

### **2.1 MAIN OBJECTIVES, PRIMARY AND SECONDARY ENDPOINTS**

#### **2.1.1 Main objectives**

The main objective of the study is investigate the effect of escalating doses of oral tyramine on systolic blood pressure (SBP) at baseline and following an oral treatment with BI 1467335 up to 39 days at a dose of 10 mg or 15 mg once daily compared to placebo and phenelzine (Nardil®) as positive control.

Further objectives are the exploratory evaluation of pharmacokinetics and the evaluation of safety and tolerability.

#### **2.1.2 Primary endpoint**

Primary endpoint of the study is the tyramine sensitivity factor (TSF), defined as ratio of the tyramine dose causing an increase of systolic blood pressure (SBP)  $\geq 30$  mmHg for at least 3 consecutive measurements (TYR30) at baseline and at steady state following multiple oral doses of BI 1467335, placebo or phenelzine.

Proprietary confidential information © 2020 Boehringer Ingelheim International GmbH or one or more of its affiliated companies

#### 2.2.2.2 Safety and tolerability

Safety and tolerability of BI 1467335 and phenelzine (Nardil®) will be assessed based on:

- Adverse events (including clinically relevant findings from the physical examination)
- Safety laboratory tests
- 12-lead ECG
- Vital signs (blood pressure, pulse rate)

### 3. DESCRIPTION OF DESIGN AND TRIAL POPULATION

### 3.1 OVERALL TRIAL DESIGN AND PLAN

In total, 62 healthy male and female subjects are planned to participate in this multiple dose study.

The primary outcome of the study will be the tyramine sensitivity factor (TSF), which is defined as the ratio of the tyramine dose causing an increase in systolic blood pressure (SBP)  $\geq 30$  mmHg for at least 3 consecutive measurements (TYR30) at baseline and following a treatment of 28 days with BI 1467335 or placebo QD, or 7 days with phenelzine BID. A treatment duration of 28 days is required for BI 1467335 to reach steady state, whereas 7 days is considered sufficient for phenelzine.

As part of the screening procedure subjects will be challenged with escalating oral doses of tyramine. Tyramine doses will be escalated from 10 mg to 700 mg QD (25, 50, 100, 200, 300, 400, 500, 600, 700 mg) on a daily basis. For each subject, the tyramine dose escalation will be stopped when an increase of systolic blood pressure (SBP)  $\geq 30$  mmHg for at least 3 consecutive measurements is measured (i.e. TYR30). Participants who will not attain the predefined target elevation in SBP within 4 hours after the highest tyramine dose (700 mg) will not be included in the study.

Subjects considered eligible to enter the study will be assigned to one of three dose groups. The three dose groups to be evaluated are outlined in [Table 3.1: 1](#).

Table 3.1: 1 Dose groups

Dose Group	1	2	3
	BI 1467335	BI 1467335	Phenelzine (Nardil®)
Daily dose (mg)	10	15	30
Posology	1-0-0	1-0-0	1-0-1
Treatment duration	Up to Day 39	Up to Day 39	Up to Day 19
Number of subjects	24	24	14
Subjects receiving placebo	8	8	0
Subjects receiving active drug	16	16	14

Dose Group 1 and 2 consists of 24 subjects each, with 16 subjects per dose group assigned to BI 1467335 (active drug) and 8 subjects assigned to placebo. Both BI 1467335 dose groups will be conducted according to a double-blind, randomised, multiple-dose, placebo-controlled within dose groups, parallel group design.

Dose Group 3 will be conducted open-label with no placebo control, and consists of 14 subjects receiving the same treatment of phenelzine as positive control (comparator).

Proprietary confidential information © 2020 Boehringer Ingelheim International GmbH or one or more of its affiliated companies

From Day 29, for the BI treatment and placebo arms, and Day 8 for the phenelzine arm, tyramine challenge will be repeated with escalating doses from 5 mg to 700 mg until TYR30 has been established. Concomitant to the tyramine challenge subjects will continue with the intake of their assigned medication, resulting in a maximum treatment duration of up to 19 days (on Day 19 intake of phenelzine only in the morning) for the phenelzine dose group and up to 39 days for the BI 1467335 dose groups.

The study will start with subjects of the phenelzine group. After completion of at least 8 subjects of the phenelzine group, subjects of all dose groups may enter the study.

An overview of all relevant trial activities is provided in the [Flow Chart](#). For visit schedule and details of trial procedures at selected visits, refer to [Sections 6.1](#) and [6.2](#), respectively.

### **3.2 DISCUSSION OF TRIAL DESIGN, INCLUDING THE CHOICE OF CONTROL GROUP**

In both BI 1467335 dose groups, double-blind conditions regarding the subject's treatment (active drug or placebo) are maintained within each dose group. Although the current dose level will be known to subjects and investigators, the risk of an observer bias with regard to dose dependent effects and the primary endpoint (TSF) is considered low. The use of placebo will allow estimating the impact of individual factors on the results of the tyramine challenge.

Phenelzine as an unselective MAO-inhibitor was consistently shown to increase TSF [[R18-2841](#)] and phenelzine was therefore selected as positive control. Because of the expected pronounced effect on TSF a reliable blinding of the phenelzine treatment is considered not applicable, and therefore this dose group will be conducted open label. The anticipated effects on TSF in the phenelzine treatment group will serve as a benchmark to conclude about effects on TSF in the BI 1467335 dose groups. As a validation of study conduct, the study will start with subjects of the phenelzine group, before subjects of the BI 1467335 dose groups may enter the study.

Dosing duration for BI 1467335 and phenelzine is considered sufficient to achieve steady-state drug exposure and to exclude transient effects.

### **3.3 SELECTION OF TRIAL POPULATION**

It is planned that 62 healthy male and female subjects (at least 30% of each sex) will enter the study. They will be recruited from the volunteers' pool of the trial site.

A log of all subjects enrolled into the trial (i.e. who have signed informed consent) will be maintained in the ISF irrespective of whether they have been treated with investigational drug or not.

#### **3.3.1 Main diagnosis for trial entry**

The study will be performed in healthy subjects.

### 3.3.2 Inclusion criteria

Subjects will only be included in the trial if they meet the following criteria:

1. Healthy male or female subjects according to the assessment of the investigator, as based on a complete medical history including a physical examination, vital signs (BP, PR), 12-lead ECG, and clinical laboratory
2. Age of 18 to 45 years (inclusive)
3. BMI of 18.5 to 29.9 kg/m^2 (inclusive)
4. Signed and dated written informed consent prior to admission to the study, in accordance with GCP and local legislation
5. Male subjects, or female subjects who meet any of the following criteria before the first administration of trial medication until 30 days after trial completion:
  - Use of adequate contraception, e.g. any of the following methods *plus* condom: implants, injectables, combined oral or vaginal contraceptives, intrauterine device (in case of oral contraceptives start of contraception at least 30 days before administration of trial medication)
  - Sexually abstinent
  - A vasectomised sexual partner (vasectomy at least 1 year prior to enrolment)
  - Surgically sterilised (including hysterectomy)
  - Postmenopausal, defined as at least 1 year of spontaneous amenorrhea (in questionable cases a blood sample with levels of FSH above 33,4 U/L and estradiol below 71,6 pmol/L is confirmatory)

Alternatively, true abstinence is acceptable when it is in line with the subject's preferred and usual lifestyle. If a subject is usually not sexually active but becomes active, with their partner, they must comply with the contraceptive requirements detailed above.

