##### *Toxicology*

The NOAEL in rats orally exposed to BI 1467335 for 13 weeks was 12.5 mg/kg. This dose corresponded to mean  $C_{max}$  and  $AUC_{0-24h}$  levels of 8430 nM and 65700 nM $\cdot$ h, respectively, in rat. The NOAEL in dogs orally exposed to BI 1467335 for 13 weeks was 3 mg/kg. This dose corresponded to mean  $C_{max}$  and  $AUC_{0-24h}$  levels of 3000 nM and 25900 nM $\cdot$ h, respectively, taken from females who the lowest plasma exposure at the NOAEL. This provides an adequate safety window between clinical exposure and exposure at NOAEL levels in animals. For further details, please refer to the current 'Investigator's Brochure (IB)' [[c04751792](#)].

These findings are consistent with results of the 4 weeks toxicology studies in rats and dogs [[n00244592](#), [n00247850](#)].

BI 1467335 does not present a genotoxic hazard.

Proprietary confidential information © 2020 Boehringer Ingelheim International GmbH or one or more of its affiliated companies

The available nonclinical safety data on embryo-fetal development in rats and rabbits support repeated oral administration of BI 1467335 to humans of non-childbearing potential for up to 13 weeks duration. However, women of childbearing potential are only allowed to participate in clinical trials after testing negative for pregnancy and under adequate contraception with two methods, of which at least one is highly effective, during the trial.

The pharmacokinetic behavior of BI 1467335 in rats and dogs was characterised by rapid absorption, a low to moderate half-life and a predominantly over proportional increase of plasma exposure over dose. The *in vitro* plasma protein binding was low in all investigated species, with  $\leq 25\%$  bound in human plasma. In vitro studies in cryopreserved human hepatocytes indicated a prevalence of oxidative O-dealkylation as primary metabolic pathway.

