#### Clinical experience

A 4-week phase I study [[c08854973](#)] investigated safety, tolerability, PK and PD of multiple doses of 10 mg, 15 mg and 20 mg q.d. administered for 28 days. The study included 36 healthy subjects (28 males, 8 females of non-childbearing potential) with 12 subjects assigned to one of three treatment groups with 9 subjects on active and 3 on placebo. Repeated doses of 10 mg, 15 mg or 20 mg BI 1467335 q.d. have been well tolerated with similar frequencies of AEs across all dose groups including placebo. The intensity of AEs was mainly mild (CTCAE grade 1), there were no SAEs.

There were no noteworthy changes in vital signs or laboratory parameters. A centralized ECG evaluation did not show any relevant individual QT prolongation, i.e. QTcF increase of greater 60 ms from baseline or an absolute QT or QTc value greater than 500 ms. Both graphical and explorative systemic BI 1467335 exposure versus QTcF, QTcN, and HR analyses did not suggest relevant drug related signals [[c16567028](#)].

The safety observed after 4 weeks is in line with results of a preceding combined SRD and MRD study [[c09036683](#)] investigating single doses of 1-20 mg BI 1467335 (HCl, corresponding to 0.885 – 17.7 mg free base) and multiple doses (14 days) of 3 to 10 mg BI 1467335 HCl q.d. (corresponding to 2.66 to 8.85 mg free base). The data are also in line with a single dose study investigating the food effect of a tablet formulation at a dose of 10 mg q.d. [[c17150058](#)].

Two further Phase I studies have been finally reported. These studies provide additional safety information to support the dose regimen of the planned study.

Study 1386-0002 [[c25844331](#)] investigated the influence of moderate renal impairment on the pharmacokinetics of multiple doses in comparison to a matched control group with

Proprietary confidential information © 2020 Boehringer Ingelheim International GmbH or one or more of its affiliated companies

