18. Intention to perform excessive physical activities within one week prior to the administration of trial medication or during the trial
19. Inability to comply with the dietary regimen of the trial site
20. A marked baseline prolongation of QT/QTc interval (such as QTc intervals that are repeatedly greater than 450 ms in males or repeatedly greater than 470 ms in females) or any other relevant ECG finding at screening
21. A history of additional risk factors for *Torsade de Pointes* (such as heart failure, hypokalaemia, or family history of Long QT Syndrome)
22. Subject is assessed as unsuitable for inclusion by the investigator, for instance, because the subject is not considered able to understand and comply with study requirements, or has a condition that would not allow safe participation in the study
23. Use of MAO inhibitors within 90 days before tyramine dosing
24. Use of fluoxetine within 5 weeks before tyramine dosing
25. Use of over-the-counter sympathomimetic or grapefruit products within 7 days before tyramine dosing
26. Subject has a known intolerance to tyramine-containing foods
27. At screening, no increase of systolic blood pressure > 30 mmHg during tyramine challenge at the highest tested dose of 700 mg tyramine

Proprietary confidential information © 2020 Boehringer Ingelheim International GmbH or one or more of its affiliated companies

Female subjects will not be allowed to participate, if any of the following apply:

28. Positive pregnancy test, pregnancy, or plans to become pregnant within 30 days after study completion
29. Lactation

For study restrictions, refer to [Section 4.2.2](#).

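### Inclusion criterion 5 accepts a vasectomised partner as the only contraceptive measure, although Section 1.2.1 asks for two methods in women of childbearing potential

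*Protocol*

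**What the plan says.** Protocol Section 1.2.1, under Toxicology, says that the embryo-fetal data "support repeated oral administration of BI 1467335 to humans of non-childbearing potential for up to 13 weeks duration". It then limits the use of the drug in other women. The first limit concerns testing: "women of childbearing potential are only allowed to participate in clinical trials after testing negative for pregnancy". The second concerns birth control, where these women must be "under adequate contraception with two methods, of which at least one is highly effective, during the trial".

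The rule that the site applies is inclusion criterion 5 in Section 3.3.2. It admits men, and "female subjects who meet any of the following criteria before the first administration of trial medication". Five bullets follow:

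- a listed contraceptive method together with a condom;
- sexual abstinence;
- "A vasectomised sexual partner (vasectomy at least 1 year prior to enrolment";
- surgical sterilisation;
- postmenopausal status.

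A closing paragraph deals with a subject who stops being abstinent and says that "they must comply with the contraceptive requirements detailed above".

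Two other places touch on the matter. Section 4.2.2.2 asks women of childbearing potential to keep up adequate contraception throughout the trial, and sends the reader to Section 3.3.2 for what counts as adequate. Exclusion criterion 28 reads "Positive pregnancy test, pregnancy, or plans to become pregnant within 30 days after study completion".

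**The concern.** Criterion 5 is an any-of list, so one bullet is enough. A fertile woman in Dose Group 1 or 2 whose partner is vasectomised is eligible on that ground alone. She is still of childbearing potential, so the condition in Section 1.2.1 still applies to her, and she does not meet it.

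An investigator who follows Section 3.3.2 exactly could therefore give BI 1467335 to a woman outside the condition that the same protocol sets for giving it. The usual checks would not show this. Because she meets criterion 5, the SAP's deviation category for unmet inclusion criteria (Table 6.2: 1, code A1) would not apply.

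What is at stake is the prevention of pregnancy during exposure, by this route only. Stopping the medication once a pregnancy is known (Section 3.3.4) and reporting exposure within 24 hours (Section 5.2.6.2.4) both come after the event.

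**Working it through.** The plan gives no figure to reproduce. The check sets the texts side by side.

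**Step 1: methods required of a woman of childbearing potential**

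| Situation | Section 1.2.1 | Criterion 5 | Agree? |
|---|---|---|---|
| Listed contraceptive | 2 | 2 (method plus condom) | Yes |
| Vasectomised partner | 2 | 1 | No, short by 2 − 1 = 1 |

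The surgical-sterilisation and postmenopausal bullets do not conflict, because those women are not of childbearing potential. Abstinence is taken up under the objection. The mismatch is therefore in 1 bullet of 5.

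The shortfall does not depend on whether a vasectomised partner counts as the highly effective method. If it does, the second method is missing. If it does not, both the second method and the highly effective one are missing.

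**Step 2: does any other text supply the second method?**

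- Section 4.2.2.2 refers back to Section 3.3.2, so it adds nothing.
- Exclusion criterion 28 covers the pregnancy test, pregnancy and pregnancy plans, but not contraception.
- The closing paragraph of criterion 5 returns a woman who stops being abstinent to the same list, where the single measure is again enough.

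None does.

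**Step 3: exposure, and what limits it**

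- Longest dosing: Day 1 to Day 39, once daily, which is 39 doses.
- Continuous hospitalisation starts on the evening of Day 25 (Flow Chart; Section 6.2.2). Doses on Days 26 to 39 are taken in-house: 39 − 26 + 1 = 14.
- Doses before that point: 39 − 14 = 25.
- Nights away from the site after the first dose, assuming discharge on Days 1, 7, 14 and 21 as scheduled: Days 1 to 24 give 24 nights. Taking off the overnight stays that begin on Days 6, 13 and 20 leaves 24 − 3 = 21.

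Thirty-nine doses is thus a ceiling on exposure. It does not measure the time during which conception could occur on treatment, which is nearer three weeks. A pregnancy conceived in that time could still be exposed to later doses.

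**Step 4: how many women?** The protocol requires at least 30% of each sex in each dose group and ages 18 to 45, so women of childbearing potential are to be expected. Nothing says how many would qualify through a vasectomised partner, so no head-count can be given.

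**The case against.** The strongest reply is that Section 1.2.1 is background. It speaks of clinical trials in general and sends the reader to the Investigator's Brochure, whereas Section 3.3.2 is the operative rule and Section 4.2.2.2 names it as the definition. The sponsor may regard a partner sterilised at least a year earlier as adequate alone. In that case the sentence in Section 1.2.1 is too broad and nobody is under-protected. This much stands: the documents do not show which text is right. It does not remove the conflict, because Section 1.2.1 states this protocol's own condition for this compound and the protocol records no exception.

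A second reply is that counting methods also fails the abstinent woman, who uses none. Counted literally, that is so. The difference, in my judgement, is that abstinence leaves no conception risk for a method to act on, while a vasectomised partner is a contraceptive measure for a sexually active woman. The documents do not give the sponsor's reasoning on either.

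Third, there are safeguards before the event: the serum pregnancy test at screening, exclusion criterion 28, the overnight stays, and hospitalisation from the evening of Day 25. These stand and lower the risk. None is a second contraceptive method, and confinement does not cover the ambulatory weeks or the time between discharge and the end-of-trial examination.

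Fourth, SAP Section 4 records that the study was permanently discontinued. A change to the criterion can no longer affect enrolment here. Its value is in making the protocol text consistent and in any reuse of that text.

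A reader might also infer from the 4-week multiple-dose study, whose population was "28 males, 8 females of non-childbearing potential", that the gap has practical effect in this trial. That does not follow. The earlier population says nothing about whether anyone here would use this route, or whether the route protects less well.

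**Conclusion.** The inconsistency is real and narrow: two methods in Section 1.2.1, one in the vasectomised-partner bullet, and no text elsewhere to reconcile them. Its safety weight is minor. The number of women affected is unknown and may be zero, and screening tests and confinement limit the risk.

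The conclusion rests on two readings: that a partner's vasectomy leaves the woman of childbearing potential, and that the condition in Section 1.2.1 applies to this trial because subjects receive BI 1467335.

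Two stronger readings should be resisted. One is that criterion 5 as a whole abandons the two-method rule; its contraceptive bullet pairs every example with a condom. The other is that the protocol has been shown to leave women inadequately protected; that would require knowing that Section 1.2.1 is the correct standard, and the documents do not settle it.

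The primary analysis, the per protocol set and the sample size are unaffected.

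**What to change.** In criterion 5, extend the vasectomised-partner bullet with wording such as *plus condom or another listed method*. A woman who stops being abstinent is then covered too, because the closing paragraph sends her to the same list.

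If the sponsor's toxicology function holds that a vasectomised partner alone is sufficient for this compound, record that exception in Section 1.2.1 instead, so that the two sections agree.

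Either way the change is about one line. Tightening the criterion might add an occasional female screening failure; amending Section 1.2.1 would add none.
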